# Clinical Study Protocol

## Johnson & Johnson Vision Care, Inc.

- Limbal cell Damage leading to Conjunctivalization

**Significant Adverse Events** – are defined as events that are symptomatic and warrant discontinuation (temporary or permanent) of the contact lens wear

Diagnoses and conditions that are considered Ocular Significant Adverse Events include, but not limited to the following:

- Contact Lens Induced Peripheral Ulcer (CLPU)
- Significant Infiltrative Events (SIE)
- Superior Epithelial Arcuate Lesions (SEALs)
- Any Temporary Loss of > 2 Lines of BSCVA
- Other grade 3 or higher corneal findings, such as abrasions or edema
- Non-contact lens related corneal events - e.g. Epidemic Keratoconjunctivitis (EKC)
- Asymptomatic Corneal Scar
- Any corneal event which necessitates temporary lens discontinuation > 2 weeks

**Non-Significant Adverse Events** – are defined as those events that are usually asymptomatic and usually do not warrant discontinuation of contact lens wear but may cause a reduction in wear time. However, the Investigator may choose to prescribe treatment as a precautionary measure.

Diagnoses and conditions that are considered Ocular Non-Significant Adverse Events include, but not limited to the following:

- Non-significant Infiltrative Event (NSIE)
- Contact Lens Papillary Conjunctivitis (CLPC)
- Superficial Punctate Keratitis (SPK)
- Conjunctivitis: Bacterial, Viral, Allergic
- Blepharitis
- Meibomianitis
- Contact Dermatitis
- Localized Allergic Reactions
- Any corneal event not explicitly defined as serious or significant adverse event, which necessitates temporary lens discontinuation < 2 weeks

**Adverse Device Effect (ADE)** – An ADE is an “adverse event related to the use of an investigational medical device.

**NOTE 1: to entry: This definition includes adverse events resulting from insufficient or inadequate instructions for use, deployment, implantation, installation, or operation, or any malfunction of the investigational medical device.**

**NOTE 2 to entry: This definition includes any event resulting from use error or from intentional misuse of the investigational medical device.”**

**Unanticipated Adverse Device Effect (UADE)** – Any serious adverse effect on health or safety or any life-threatening problem or death caused by, or associated with, the test article,

# Clinical Study Protocol

## Johnson & Johnson Vision Care, Inc.

if that effect, problem, or death was not previously identified in nature, severity, or degree of incidence in the investigational plan, Investigator's Brochure or protocol, or any other unanticipated serious problem associated with the test article that relates to the rights, safety and welfare of subjects.

### 13.2. Assessing Adverse Events

In conjunction with the medical monitor, the Investigator will evaluate adverse events to ensure the events are categorized correctly. Elements of categorization will include:

- Seriousness/Classifications (see definition in Section 13.1).
- Causality or Relatedness – i.e. the relationship between the test article, study treatment or study procedures and the adverse event (not related; unlikely related; possibly related; related - see definition in Section 13.2.1).
- Adverse Event Severity – Adverse event severity is used to assess the degree of intensity of the adverse event (mild; moderate; severe for all events - see definition in Section 13.2.2).
- Outcome – not recovered or not resolved; recovering or resolving; recovered or resolved with sequelae; recovered or resolved; death related to adverse event; unknown.
- Actions Taken – none; temporarily discontinued; permanently discontinued; other.

#### 13.2.1. Causality Assessment

**Causality Assessment** – A determination of the relationship between an adverse event and the test article. The test article relationship for each adverse event should be determined by the investigator using these explanations:

- Not Related- An adverse event that is not related to the use of the test article, study treatment or study procedures.
- Unlikely Related – An adverse event for which an alternative explanation is more likely, e.g. concomitant treatment, concomitant disease(s), or the relationship of time suggests that a causal relationship is not likely.
- Possibly Related – An adverse event that might be due to the use of the test article, or to the study treatment or study procedures. An alternative explanation, e.g. concomitant treatment, concomitant disease(s), is inconclusive. The relationship in time is reasonable. Therefore, the causal relationship cannot be excluded.
- Related – An adverse event that is listed as a possible adverse effect (device) or adverse reaction (drug) and cannot be reasonably explained by an alternative explanation, e.g. concomitant treatment of concomitant disease(s). The relationship in time is very suggestive, e.g. it is confirmed by de-challenge and re-challenge.

#### 13.2.2. Severity Assessment

**Severity Assessment** – A qualitative assessment of the degree of intensity of an adverse event as determined by the Investigator or reported to him/her by the subject. The assessment of severity is made irrespective of test article, study treatment or study procedure relationship or seriousness of the event and should be evaluated according to the following scale:

# Clinical Study Protocol

## Johnson & Johnson Vision Care, Inc.

- Mild – Event is noticeable to the subject, but is easily tolerated and does not interfere with the subject’s daily activities.
- Moderate – Event is bothersome, possible requiring additional therapy, and may interfere with the subject’s daily activities.
- Severe – Event is intolerable, necessitates additional therapy or alteration of therapy and interferes with the subject’s daily activities.

### 13.3. Documentation and Follow-Up of Adverse Events

The recording and documenting of adverse events (ocular and non-ocular) begin when the subjects are exposed to the test article, study treatment or study procedure. Adverse events reported before the use of test article, start of study treatment, or study procedures will be recorded as medical history. However, if the condition deteriorates at any time during the study it will be recorded and reported as an AE. Untoward medical events reported after the subject’s exit from the study will be recorded as adverse events at the discretion of the Investigator.

Upon finding an adverse event, the Principal Investigator will document the condition in the subject record and in the eCRFs. He/she will complete the Adverse Event /eCRF.

Complete descriptions of all adverse events must be available in the subject record. All Adverse Events including local and systemic reactions not meeting the criteria for “serious adverse events” shall be captured on the appropriate case report form or electronic data system. All adverse events occurring while the subject is enrolled in the study must be documented appropriately regardless of relationship.

It is the Investigator’s responsibility to maintain documentation of each reported adverse event. All adverse events will be followed in accordance with applicable licensing requirements. Such documentation will include the following:

- Adverse event (diagnosis not symptom).
- Drawings or photographs (where appropriate) that detail the finding (e.g., size, location, and depth, etc.).
- Date the clinical site was notified.
- Date and time of onset.
- Date and time of resolution.
- Adverse event classification, severity, and relationship to test articles, as applicable.
- Treatment regimen instituted, including concomitant medications prescribed, in accordance with applicable licensing requirements.
- Any referral to another health care provider if needed.
- Outcome, ocular damage (if any).
- Likely etiology.
- Best corrected visual acuity at the discovery of the event and upon conclusion of the event, if related to the visual system.

In addition, if an infiltrate(s) is present, he/she will complete the Corneal Infiltrate Assessment eCRF. Where necessary, a culture of the corneal lesion will be collected to determine if the

# **Clinical Study Protocol**

## **Johnson & Johnson Vision Care, Inc.**

infection is microbial in nature. If cultures are collected, the date of culture collection and laboratory utilized will be recorded.

Changes in the severity of an AE shall be documented to allow an assessment of the duration of the event at each level of intensity to be performed. Adverse events characterized as intermittent require documentation of the onset and duration of each episode. Changes in the assessment of relationship to the Test Article shall also be clearly documented.

Subjects who present with an adverse event shall be followed by the Investigator, within licensure, until all signs and symptoms have returned to pre-treatment status, stabilized, or been satisfactorily resolved. If further treatment beyond licensure is required, the patient will be referred to the appropriate health care provider. The Investigator will use his/her clinical judgment as to whether a subject reporting with an adverse event will continue in the study. If a subject is discontinued from the study, it will be the responsibility of the Investigator to record the reason for discontinuation. The Investigator will also document the adverse event appropriately and complete the Adverse Event eCRF. Any subjects with ongoing adverse events related to the test article, study treatment or study procedures, as of the final study visit date, should be followed to resolution of the adverse event or until referral to an appropriate health care provider, as recommended by the Investigator. Non-ocular adverse events that are not related to the test article, study treatment, or study procedures may be recorded as “ongoing” without further follow-up.

### **13.4. Reporting Adverse Events**

The Investigator will notify the Sponsor of an adverse event by e-mail, facsimile, or telephone as soon as possible and no later than 24 hours from discovery for any serious /significant adverse events, and 2 days from discovery for any non-significant adverse event. In addition, a written report will be submitted by the Principal Investigator to the IEC/IRB according to their requirements (Section 13.4.2). The report will comment whether the adverse event was considered to be related to the test article, study treatment or study procedures.

#### **13.4.1. Reporting Adverse Events to Sponsor**

##### **Serious/Significant Adverse Events**

The Investigator will inform the sponsor of all serious/significant adverse events occurring during the study period as soon as possible by e-mail, fax, or telephone, but no later than 24 hours following discovery of the event. The Investigator is obligated to pursue and obtain information requested by the Sponsor in addition to that information reported on the eCRF. All subjects experiencing a serious/significant adverse event must be followed up and all outcomes must be reported.

When medically necessary, the Investigator may break the randomization code to determine the identity of the treatment that the subject received. The Sponsor and study monitor should be notified prior to unmasking the test articles.

In the event of a serious/significant adverse event, the Investigator must:

- Notify the Sponsor immediately.

# **Clinical Study Protocol**

## **Johnson & Johnson Vision Care, Inc.**

- Obtain and maintain in the subject's records all pertinent medical information and medical judgment for colleagues who assisted in the treatment and follow-up of the subject.
- Provide the Sponsor with a complete case history which includes a statement as to whether the event was or was not related to the use of the test article.
- Notify the IEC/IRB as required by the IEC/IRB reporting procedure according to national regulations.

### **Unanticipated (Serious) Adverse Device Effect (UADE)**

In the event of an Unanticipated (Serious) Adverse Device Effect (UADE), the Investigator will submit a report of the UADE to the Sponsor and IEC/IRB as soon as possible, but no later than 24 hours after the Investigator first learns of the effect. This report is in addition to the immediate notification mentioned above.

The Sponsor must conduct an evaluation of the UADE and must report the results of the evaluation to FDA, the IEC/IRB and participating Investigators within 10 working days after the Sponsor first receives notification of the effect.

### **Non-Serious Adverse Events**

All non-serious adverse events, including non-serious adverse device effects, will be reported to the sponsor by the Investigator no later than 2 days from discovery.

#### **13.4.2. Reporting Adverse Events to the Responsible IEC/IRB and Health Authorities**

Adverse events that meet the IEC/IRB requirements for reporting must be reported within the IEC/IRB's written guidelines. Each clinical site will refer to and follow any guidelines set forth by their Approving IEC/IRB. Each clinical site will refer to and follow any guidelines set forth by their local governing Health Authorities.

The Sponsor will report applicable Adverse Events to the local health authorities according to the written guidelines, including reporting timelines.

#### **13.4.3. Event of Special Interest**

Not applicable

### **13.5. Reporting of Pregnancy**

Subjects reporting pregnancy (by self-report) during the study will be discontinued after the event is recorded as an Adverse Event. Once discontinued, pregnant participants and their fetuses will not be monitored for study related purposes.

Pregnant participants are not discontinued from contact lens or solution related studies for safety concerns, but due to general concerns relating to pregnancy and contact lens use. Specifically, pregnant women are discontinued due to fluctuations in refractive error and/or visual acuity that occur secondary to systemic hormonal changes, and not due to unforeseen health risks to the mother or fetus.

# Clinical Study Protocol

## Johnson & Johnson Vision Care, Inc.

### 14. STATISTICAL METHODS

#### 14.1. General Considerations

Statistical analysis will be undertaken by the study biostatistician. A general description of the statistical methods to be implemented in this clinical trial is outlined below.

All data summaries and statistical analyses will be performed using the SAS software Version 9.4 (SAS Institute, Cary, NC). Throughout the analysis of data, the results for each subject/eye will be used when available for summarization and statistical analysis.

Summary tables (descriptive statistics and/or frequency tables) will be provided for all baseline variables, efficacy variables, and safety variables as appropriate. Continuous variables will be summarized with descriptive statistics (n, mean, standard deviation [SD], median, minimum and maximum). Frequency count and percentage of subjects or eyes within each category will be provided for categorical data.

#### 14.2. Sample Size Justification

Approximately 50 eligible subjects will be enrolled to target approximately 40 subjects to complete the study. The sample size was calculated to test both the primary hypothesis with a 2-sided type I error of 5% and a minimum of power of 80%.

Based on historical data from [REDACTED] where the same Test lens was utilized, the proportion of eye at lens fitting for distance monocular high luminance high contrast was 0.995 and the correlation between the left and right eyes was 0.627. Using this information the total number of subjects needed to achieve the primary hypothesis is 34 subjects. To account for subject dropout this study will target to enroll approximately 50 subjects with the aim to complete approximately 40 subjects.

#### 14.3. The POWER procedure was used to conduct the power analysis for both the primary and secondary endpoint. The total number of subjects needed to test both the primary and secondary hypothesis is 39. Analysis Populations

##### **Safety Population:**

All subjects who were administered any test article excluding subjects who drop out prior to administering any test article. At least one observation should be recorded.

##### **Per-Protocol Population:**

All subjects who have successfully completed all visits and did not substantially deviate from the protocol as determined by the trial cohort review committee prior to database hard lock (Per-Protocol Population). Justification of excluding subjects with protocol deviations in the Per-Protocol Population set will be documented in a memo to file.

##### **Intent-to-Treat (ITT) Population:**

All randomized subjects regardless of actual treatment and subsequent withdrawal from study or deviation from protocol. At least one observation should be recorded.

# Clinical Study Protocol

## Johnson & Johnson Vision Care, Inc.

### 14.4. Level of Statistical Significance

All planned analysis for this study will be conducted with an overall type I error rate of 5%.

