# Clinical Study Protocol

## Johnson & Johnson Vision Care, Inc.

### SYNOPSIS

Protocol Title	Clinical Evaluation of Daily Disposable Etafilcon A Cosmetic Contact Lenses
Sponsor	JJVC, [name]
Clinical Phase	Confirmatory phase, Phase 3
Trial Registration	This study will be registered on ClinicalTrials.gov based on the following: confirmatory study meets the requirements for registration.
Test Article(s)	Investigational Products: etafilcon A with cosmetic pattern
Wear and Replacement Schedules	Wear Schedule: Daily Wear Replacement Schedule: Daily Disposable
Objectives	
The primary objective of this study is to evaluate high luminance/high contrast visual performance (Logarithm of Minimal Angle of Resolution [logMAR]) of two investigational cosmetic lenses at lens fitting.
 
Additional assessments will include:
 
 
• Subjective Vision (CLUE)
 
• Subjective Comfort (CLUE)
 
• Subjective Handling (CLUE)
 
• logMAR objective vision (high luminance/low contrast and low luminance/high contrast)
 
• Mechanical Lens fit
 
• Cosmetic Lens fit/Hula Hoop
 
• Ocular Physiology
 

Study Endpoints	
Primary endpoint: LogMAR visual acuity at fitting using ETDRS charts (CTP-2059).
 
Other observations (descriptively summarized for each lens type) will include: Subjective Vision (CLUE) Subjective Comfort (CLUE) Subjective Handling (CLUE) logMAR objective vision (high luminance/low contrast and low luminance/high contrast) Mechanical Lens fit Cosmetic Lens fit/Hula Hoop Ocular Physiology

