### 2.3. Hypotheses

#### Primary Hypothesis

1. The proportion of eyes with corrected distance monocular visual acuity 0.176 logMAR or better (ie, Snellen VA 20/30 or better) using the Test lenses under high illumination/high contrast is superior to 90%.

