# Clinical Study Protocol

## Johnson & Johnson Vision Care, Inc.

same subject across study periods will be modeled using either homogenous compound symmetry (CS) or unstructured (UN). The structure that returns the lowest finite-sample corrected Akaike's Information criterion will be selected as the structure that best fits the model. The Kenward and Roger method, will be used for the denominator degrees of freedom.

Comparisons between the Test and Control will be carried out using 2-sided 95% confidence intervals constructed for the least-square means (Test minus Control) at the 1-week follow-up evaluation. The null and alternative hypothesis for CLUE vision scores to test for non-inferiority of the Test lens relative to the Control lens is as follows:

$$H_0: \mu_{Test} - \mu_{Control} \leq -5$$
$$H_A: \mu_{Test} - \mu_{Control} > -5$$

Non-inferiority will be declared if the lower limit of the 95% confidence interval for the least-square mean difference is greater than -5. i.e.  $P(\mu_{Test} - \mu_{Control} > -5) \geq 0.975$ .

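### Section 14.7 lets CLUE vision non-inferiority be declared regardless of the primary, although the synopsis, 2.3 and 14.6 allow for no such claim and 14.4 does not say how it shares the 5%

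*Combined protocol and SAP*

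**What the plan says.** - **Section 14.4** sets the error rate for everything planned: "All planned analysis for this study will be conducted with an overall type I error rate of 5" per cent. It exempts nothing and gives no order of testing and no split of alpha.
- **Section 14.2** sizes the study for the primary hypothesis "with a 2-sided type I error of 5% and a minimum of power of 80" per cent.
- **Section 2.3** lists one hypothesis, that the proportion of eyes reaching the acuity threshold "using the Test lenses under high illumination/high contrast is superior to 90" per cent. **Section 14.5** declares it met if the lower 95% limit for that proportion is above 90%.
- **Section 14.6** contains no secondary analysis.
- **Section 14.7** is headed as exploratory. Under CLUE Scores it gives CLUE vision a null and an alternative hypothesis, a margin of -5 points and a rule: "Non-inferiority will be declared if the lower limit of the 95% confidence interval for the least-square mean difference is greater than -5". The rule does not depend on the primary result.
- **Synopsis, Study Endpoints**, introduces the list that includes the CLUE scores with: "Other observations (descriptively summarized for each lens type) will include".
- **The heading of Section 14.3** carries a stray sentence: "The total number of subjects needed to test both the primary and secondary hypothesis is 39". No secondary hypothesis is defined anywhere in the current text.

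**The concern.** The plan gives CLUE vision two incompatible roles. In the synopsis it is a descriptive observation, and Sections 2.3 and 14.6 leave no room for a claim. In Section 14.7 it has a margin and a decision rule worded in parallel with the primary rule of Section 14.5. A reader of the final report could not tell from the plan whether a declared CLUE vision non-inferiority is a finding of the trial or an exploratory remark.

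This matters more than usual because the primary hypothesis compares the Test lens with a fixed 90%, not with the Control lens. The CLUE vision rule is the only formal Test-versus-Control hypothesis in a randomized crossover that the synopsis labels confirmatory. As written, the primary could fail and the trial could still declare CLUE success, while Section 14.4 implies that all claims sit under one 5% allowance.

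**Working it through.** **Inputs**

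- Primary rule (14.5): lower 95% limit above 90%, so one-sided 2.5%.
- CLUE vision rule (14.7): lower 95% limit above -5, so one-sided 2.5%.
- Overall rate (14.4): 5%. Primary sizing (14.2): two-sided 5%, power at least 80%.
- Primary planning values (14.2): the proportion "was 0.995 and the correlation between the left and right eyes was 0.627"; the null value is 0.90.

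**1. The plan's own figure.** Section 14.2 says that "the total number of subjects needed to achieve the primary hypothesis is 34 subjects".

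- Design effect for two eyes: 1 + 0.627 = 1.627.
- Effective eyes: 34 × 2 / 1.627 = 68 / 1.627 = 41.8.
- Exact binomial test, upper tail 2.5%: power is 0.814 with 41 effective eyes and 0.810 with 42.

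The stated 80% is therefore reproduced for the primary alone. As a minimum, 34 is not what the other formulas tried return (the two-sided normal approximation gives 38), but nothing below depends on that.

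**2. How many claims can be declared.** Two: the primary and CLUE vision. The other CLUE domains are modelled and get intervals, but 14.7 writes no hypothesis or margin for them.

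**3. Chance of at least one false declaration, both nulls true**

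| Counting | Independent tests | Upper bound, any dependence |
|---|---|---|
| Two one-sided 2.5% rules, as written | 1 - 0.975² = 4.94% | 2.5% + 2.5% = 5.0% |
| Two two-sided 5% tests (convention of 14.2) | 1 - 0.95² = 9.75% | 5% + 5% = 10% |

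Positive correlation between the two test statistics lowers the one-sided figure: 4.54% at 0.5 and 3.90% at 0.8 (bivariate normal). Against the primary's own one-sided 2.5%, the ratio is at most 5.0 / 2.5 = 2.

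**4. With a gate.** Suppose CLUE vision is tested only after the primary succeeds.

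- If the primary null is true, any false declaration requires a false primary success first, so the chance is at most 2.5%.
- If the primary null is false, only the CLUE claim can be false, again at most 2.5%.

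If 14.7 makes no claim at all, the primary is the only declaration and the bound is the same 2.5% one-sided (5% on the two-sided convention).

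**5. The 39 subjects.** This cannot be checked, because the visible text gives no SD for the CLUE difference. Assuming a paired non-inferiority t-test with margin 5 and true difference 0, 39 subjects correspond to an SD of differences of about 10.9 for 80% power or 9.4 for 90%. Nothing in the current text ties the 39 to the CLUE rule.

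**The case against.** The strongest reply is that CLUE is non-confirmatory almost everywhere. It is an other observation in the synopsis, an other endpoint in 2.2, absent from 2.3, and placed under an exploratory heading in 14.7. The empty 14.6 agrees with that. Exploratory analyses do not normally need alpha control, and the only two declaration rules happen to add up to no more than the 5% that 14.4 promises.

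Much of this stands. It narrows the problem to the declaration rule in 14.7 and the unrestricted wording of 14.4. It does not remove it: a preset margin with a rule for declaring success is the language of a claim, 14.4 makes no exception for exploratory work, and the synopsis limits CLUE to description.

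A reader might infer three stronger points that the documents do not support:

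- **That the overall error must exceed 5%.** Both rules work in one direction, so for the two of them 5.0% is the ceiling. It is passed only on the two-sided count.
- **That comfort and handling add further tests.** They get intervals but no hypothesis, margin or rule. An interval is not a claim.
- **That the CLUE test is underpowered.** The only SD given is a population value of 20 in Section 2.2, and there is no within-subject correlation or SD of differences. Power cannot be judged from the documents, and low power would not raise the type I error in any case.

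**Conclusion.** The concern holds in a limited form. The plan contains a rule for declaring CLUE vision non-inferiority that its synopsis, hypotheses and secondary-analysis section do not provide for, that does not depend on the primary, and whose share of the overall 5% is never stated.

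The cost in error rate is modest: up to 5.0% instead of 2.5% on the one-sided count, or up to 10% instead of 5% on the two-sided count. The more practical consequence is that a comparative claim could follow a failed primary. These figures assume that both nulls are true and that both 95% intervals have their nominal coverage. The independent-test figures also assume independence; the bounds do not. The primary conclusion is not affected.

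The sentence about 39 subjects is best read as a drafting leftover. The list of tables names a table of historical CLUE vision scores, which suggests that CLUE vision may once have been the secondary hypothesis. That is an inference, since the table does not appear in the visible text.

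**What to change.** 1. **Section 14.4:** limit the 5% (two-sided) to the single primary hypothesis.
2. **Section 14.7:** replace the CLUE vision declaration rule with the Test minus Control estimate and its 95% interval, with no claim attached. This matches the synopsis, 2.3 and 14.6.
3. **Only if the sponsor wants a CLUE vision claim:** test it solely after the primary succeeds, state that order in 14.4, and list it as a secondary hypothesis in the synopsis, 2.3 and 14.6.
4. **Heading of Section 14.3:** correct or remove the 39 subjects for a primary and secondary hypothesis. If route 3 is taken, give the SD and assumptions behind whatever number is kept.

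The choice between routes 2 and 3 should be made before unmasking, so that it cannot depend on the results. The cost is wording only. The primary test, its alpha and its sample size stay as they are. The one loss is that no stand-alone CLUE claim can be made if the primary fails; under route 2 there is no CLUE claim at all.
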